Imiquimod will be dispensed in boxes containing 18 vaginal suppositories (treatment weeks 1-8) at the beginning of the treatment course. During follow up visit at week 8 (see below), subjects will be provided a new box of 24 vaginal suppositories to complete treatment course for weeks 9-16. Study drug will be prescribed by the investigator and may be dispensed either by the investigator or study staff.

6.2.2 Follow-up Visits: Follow-up visits will occur at week 8 (between weeks 7-9), at week 16 (between weeks 16-18) and once at week 22 (between weeks 20-24). For subjects randomized to treatment arms (2) Imiquimod only and (3) Imiquimod + HPV vaccine, the week 22 visit will occur at least 3 weeks after last dose of therapy. Urine pregnancy test will be performed at all follow-up visits. Subjects with exam findings concerning for worsening disease at any point in the study will be taken out of the study and treated with surgical excision procedure.

Week 8 (7-9 weeks) Visit: This visit will be timed to occur part way through the 16 week imiquimod treatment course. For women using imiquimod (Imiquimod only and Imiquimod + HPV vaccine arms), a review of medication diary, monitoring of correct use of study medication, and report of local and systemic side effects using a standardized case report form will occur at all follow up visits. For women who received HPV vaccine as part of study protocol (Imiquimod + HPV vaccine arm), a review of vaccination diary and report of local and systemic side effects using a standardized case report form will occur at all follow up visits. A pelvic exam with colposcopy will be performed to objectively assess for gross cervical lesions in all subjects and also for local side effects from imiquimod use in the Imiquimod only and Imiquimod + HPV vaccine arms. Endocervical cytobrush samples will be obtained at this time for study purposes. Cervical biopsies will be performed as clinically indicated. Blood sample collections will also occur. In addition, women in the Imiquimod + HPV vaccine groups who were previously unvaccinated will receive their booster dose of the HPV vaccine.

Week 16 (16-18 weeks) Visit: This visit will be timed to occur at completion of imiquimod treatment course. For women using imiquimod (Imiquimod only and Imiquimod + HPV vaccine

HIC#: 1603017415 Protocol version 11.0

CIN 2/3

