10.0 EVALUATION CRITERIA

10.1 Objective Response

The major parameters of response to be assessed include treatment efficacy defined as histologic regression of cervical dysplasia to CIN 1 or less 12 to 16 weeks after the end of imiquimod treatment, HPV clearance and treatment tolerance.

- 10.11 Histologic regression: Only subjects with histologically confirmed CIN 2,3 as reviewed by a central study pathologist will be enrolled in the study. All index biopsy sites noted to have CIN 2,3 at baseline must be assessed via colposcopy. Cervical biopsy at the final colposcopy will be collected from the worst areas of residual disease. Included in the evaluations are the following criteria:
 - Histologic regression (HR): Histologic regression of all index lesions to CIN 1 or less at 12 to 16 weeks after end of imiquimod treatment period.
 - Histologic remission (HM): Complete regression of cervical dysplasia at all index biopsy sites at 12 to 16 weeks after end of imiquimod treatment period.
 - Persistent Disease (PR): One or more index lesions persists with CIN 2,3 high grade dysplasia or new lesions are identified colposcopically and histologically confirmed to be CIN 2,3.
 - Progressive Disease (PD): Worsening histology of an index lesion.
- 10.12 HPV Clearance: HPV clearance will be measured by both the Roche cobas HPV Test utilized by pathology concomitant with the pap test at final study visit which assesses for presence of 14 high risk HPV types as well as HPV 16/18 genotyping performed by [name] Lab.
- 10.13 Treatment Tolerance: The grade level of the various toxicities will be classified using the Common Toxicity Criteria, version 4 (CTC, v.4) guidelines. Acute toxicities will be scored if occurring </= 30 days from treatment completion, and chronic if > 30 days. Frequency and duration of treatment interruptions due to the treatment toxicity will be assessed.

11.0 **DURATION OF STUDY**

11.1 This study will continue as long as treatment protocols remain activated.

HIC#: 1603017415 Protocol version 11.0

CIN 2/3

11.2 The subject will be followed with routine clinical care with a 6 month colposcopy and cytology if histologic remission or regression noted at final study visit and in 12 months if cytology remains negative with normal colposcopy. Any abnormal cytology or colposcopy at 6 months should prompt cervical biopsy and management per guidelines of American Society for Colpsocpy and Cervical Pathology (ASCCP).

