15.2 Analysis Set Definitions

- **full analysis set**—all randomized subjects
- safety analysis set—all subjects who have received at least one dose of any study drug, and/or have had any assessments at baseline or later that could be associated with an AE; analyzed by treatment received
- ITT analysis set—all randomized subjects with valid baseline measurements; analyzed by treatment assigned
- modified ITT analysis set—all randomized subjects with valid baseline measurements, receiving at least one dose of any study drug, and have at least one valid post-baseline measurement of outcome; analyzed by treatment assigned

HIC#: 1603017415 Protocol version 11.0

- modified ITT completers analysis set—all randomized subjects who receive at least one dose of
 any study drug and have complete and valid post-baseline assessments of outcome; analyzed by
 treatment assigned
- **per protocol analysis set**—all randomized subjects who receive all doses of their assigned study drug, have complete and valid post-baseline assessments of outcome, and have no protocol deviations (e.g. dose modification, assessment outside of time window, non-compliance)

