Exact binomial probabilities for α given minimum required power = (1- β)								
Δ =	0.00	0.10	0.20	0.30	0.32	0.35	0.37	0.40
(1-β) ≥ 0.80	0.8080	0.8008	0.8101	0.8126	0.8011	0.8168	0.8119	0.8113
α =	0.5321	0.7745	0.1537	0.0366	0.0220	0.0118	0.0058	0.0027
(1-β) ≥ 0.90	0.9033	0.9009	0.9049	0.9060	0.9068	0.9062	0.9012	0.9009
α =	0.4835	0.6574	0.2876	0.0863	0.0616	0.0363	0.0203	0.0103
Exact binomi	Exact binomial probabilities for power = $(1-\beta)$ given maximum required α							
Δ =	0.00	0.10	0.20	0.30	0.32	0.35	0.37	0.40
α ≤ 0.025	0.0147	0.0147	0.0143	0.0140	0.0140	0.0143	0.0146	0.0149
1-β =	0.0147	0.1050	0.3472	0.6860	0.7472	0.8269	0.8706	0.9215
α ≤ 0.05	0.0305	0.0327	0.0272	0.0304	0.0317	0.0330	0.0331	0.0323
1-β =	0.0305	0.1795	0.4847	0.7870	0.8328	0.8898	0.9197	0.9535

Software: G*Power version 3.1.9.2, ©1992-2014, Franz Faul, Universität Kiel, Germany

At 7-8 months from time of initial CIN 2,3 diagnosis, persistent or progressing dysplasia will be surgically excised per current standard of care. Risk of progression of high-grade cervical dysplasia during the study period in the observation group is very low and observation periods of 6-9 months for CIN 2,3 are commonly described in the literature.^{24,39} In this regard, studies estimating the risk of clinical progression from CIN2/3 lesions to cervical cancer found that the median time was 23.5 years with only 1.6% of these lesions becoming invasive within 10 years⁴⁰. In addition, any clinical concern for disease progression based on history, physical exam or colposcopy at an interval follow up visit will trigger cervical biopsies to objectively evaluate histopathology and, should disease progression be noted, the subject will be removed from study and offered surgical excision. We will also employ early stopping rules as follows:

Evaluability for Efficacy and Toxicity:

Only those subjects who are deemed "ineligible" will be eliminated from the analysis. All subjects who receive any therapy will be evaluated for both treatment efficacy and toxicity. While on occasion, circumstances may prevent the determination of treatment efficacy, such subjects will be included in the

HIC#: 1603017415 Protocol version 11.0

analysis and labeled as "unknown". This category will be listed and be reflected in the calculation of the response rate.

References

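### Sections 6.2.2 and 15.8 differ on whether biopsy must precede removal for worsening, and 15.2 and 15.8 differ on whether a woman so removed stays in the main analysis

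*Combined protocol and SAP*

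**What the plan says.** All references are to the combined protocol and SAP.

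**Removal.** Section 6.2.2 (Follow-up Visits): "Subjects with exam findings concerning for worsening disease at any point in the study will be taken out of the study". The same sentence has them treated by surgical excision. Biopsies at weeks 8 and 16 are left to clinical indication. Section 15.8 (Sample Size Justification) sets out a sequence: "any clinical concern for disease progression based on history, physical exam or colposcopy at an interval follow up visit will trigger cervical biopsies", and then "should disease progression be noted, the subject will be removed from study and offered surgical excision". It also states: "Risk of progression of high-grade cervical dysplasia during the study period in the observation group is very low".

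**Outcome.** Section 10.11 has the category "Progressive Disease (PD): Worsening histology of an index lesion", with no time window. The primary outcome biopsy is at weeks 20-24 (1.1, 5.1, 6.2.2).

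**Analysis.** Section 15.5 runs the co-primary tests on the modified ITT set. Section 15.2 limits that set to subjects who, among other conditions, "have at least one valid post-baseline measurement of outcome". Section 15.1 rules out imputation. The evaluability text at the end of 15.8 excludes only ineligible subjects. It says that where "circumstances may prevent the determination of treatment efficacy, such subjects will be included in the" analysis under the label unknown, and adds: "This category will be listed and be reflected in the calculation of the response rate". Section 15.5 neither repeats nor cites this.

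**The concern.** There are two linked conflicts.

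1. **Trigger.** A clinician who follows 6.2.2 as written can remove and excise on an exam impression. The safeguard sits in the sample-size section, where clinic staff are unlikely to look. Each woman's CIN 2/3 is already confirmed, so what goes unconfirmed is the worsening. She may lose the rest of her observation time and have an excision she could have avoided, and section 2.0 gives the obstetric risk of excision as a reason for the trial.

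2. **Analysis.** The plan does not define a valid outcome, and no text says whether an interim biopsy or an excision specimen is one. For a woman removed early, 15.2 with 15.1 can take her out of the denominator while 15.8 keeps her in. Removal for worsening is related to the outcome. Dropping treated non-regressors raises the treated rate and inflates the effect. Dropping control non-regressors raises the control rate and shrinks the effect in both comparisons, because they share the control arm. With two rules on paper, the choice could be made after results are known.

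Removal could also differ by arm. The control is observation without placebo, only the pathologists are described as blinded, and imiquimod causes local inflammation (7.2.2.1). That is an inference; the documents give no data on it.

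**Working it through.** **The texts side by side, for a woman with a worrying exam at week 8**

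| Step | 6.2.2 with 15.2 and 15.1 | 15.8 |
|---|---|---|
| Biopsy before removal | Allowed, not required | Required |
| Removal | On exam concern | Only if progression is noted |
| Excision | Stated as done | Offered |
| Main analysis if no valid outcome | Dropped | Kept as unknown, reflected in the response rate |

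**Inputs.** Control regression 0.28, treated 0.28 + 0.35 = 0.63, 38 per arm (15.8). One-sided Fisher exact test at 0.025 (15.5). The removal probability r is assumed, because the documents give none. Removed women are taken to be non-regressors. Controls are taken to be in the modified ITT set, as 15.5 must intend, although the dose condition in 15.2 read literally would exclude them.

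**Plan's own figures.** Enumerating both binomials gives error 0.0147 at no effect and power 0.8269 at a difference of 0.35. Both match the table in 15.8.

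**Removed women dropped, one arm affected.** The number left is m ~ Bin(38, 1 − r), and regressors among them are Bin(m, p/(1 − r)). At r = 0.02 about 38 × 0.02 = 0.76 women are removed, and the affected rate moves from 0.28 to 0.28/0.98 = 0.286.

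| r | Error, treated arm only (0.28 in both arms) | Power, control arm only (0.63 vs 0.28) |
|---|---|---|
| 0 | 0.0147 | 0.827 |
| 0.01 | 0.0156 | 0.823 |
| 0.02 | 0.0165 | 0.816 |
| 0.05 | 0.0199 | 0.784 |

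If the 46 recruited per arm absorb the removals and 38 are still analysed, 2% gives error 0.0169 or power 0.812. Equal removal of 2% in both arms gives error 0.0140 and power 0.843, so it does no harm to either. Error first exceeds 0.025 between 8% (0.0243) and 9% (0.0260) treated-only removal.

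**Chance that the choice of rule changes the verdict.** This compares dropping with counting as not regressed, given that the removals have occurred in one arm.

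| Removed | 63% vs 28% | 57% vs 28% |
|---|---|---|
| One treated | 0.053 | 0.079 |
| One control | 0.001 | 0.006 |
| Two control | 0.063 | 0.078 |

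Weighted by the chance of any removals at 63% vs 28%, the figures are 1.7% (treated) and 0.4% (control) at r = 0.01, and 3.0% and 1.2% at r = 0.02.

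**A borderline case.** 20/38 vs 11/38 gives p = 0.0305. Dropping one treated non-regressor, 20/37 vs 11/38, gives p = 0.0239, which crosses 0.025.

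**The case against.** The strongest reply is that the documents largely settle both matters. The sentence in 6.2.2 is a summary, biopsies at interim visits are provided for, and 15.8 supplies the sequence. On the analysis side, biopsy-proven worsening is already Progressive Disease under 10.11. Modified ITT asks for one valid outcome where the completers set asks for complete ones, so a woman with an interim biopsy probably stays in. What remains is an undefined word and a rare event.

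Much of this stands. A reader might infer that the plan discards women with proven progression; for the reasons just given, the text does not support that. A reader might also infer that women are excised without histology. Sections 3.1.1 and 3.1.4 require confirmed CIN 2/3 at entry, and section 2.0 describes excision as generally favored in the U.S., so only the worsening is unconfirmed.

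Two things do not fall away. Section 6.2.2 as written still permits removal that 15.8 does not, and nothing says which section governs. For a woman removed without biopsy, or with a specimen not accepted as an outcome, 15.2 and 15.8 still give different denominators. The reach of 15.8 to controls is also unclear, because its sentence on evaluation speaks of subjects who receive therapy.

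It is fair, too, that counting every removal as a failure could misclassify a woman whose specimen shows CIN 1 or less, perhaps more often in the imiquimod arms. The specimen reading as main outcome would be defensible. The plan has to choose one rule in advance.

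**Conclusion.** The inconsistency is real on both points and should be corrected, but the likely numerical effect is small. At an assumed 2% removal in one arm, error is 0.0165 against 0.0147, or power 0.816 against 0.827. At 5% it is 0.0199 or 0.784, and error is still under 0.025. These figures assume that removed women are non-regressors, that removal falls in one arm only, and that none of their specimens is accepted as an outcome.

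A reader might infer a large bias, or one that favours treatment. The documents support neither. They give no removal rate and call progression under observation very low, the direction depends on which arm loses more women, and equal removal does no harm to error or power. Rates of 10-20% can be computed but carry no weight. The case for change rests on the conflicting text, on a possibly avoidable excision, and on an unsettled rule that one or two women could turn into a different verdict when a co-primary test is borderline.

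**What to change.** 1. In 6.2.2, use the sequence from 15.8: exam concern, then biopsy, then removal and an offer of excision if progression is found.
2. In 15.2, 15.5 and 15.6, state that any randomized subject in any arm, including observation, who is removed or excised for worsening before weeks 20-24 stays in the main analysis as not regressed and not in remission. Word the unknown category in 15.8 to match.
3. Send the interim biopsy or excision specimen to the blinded central review, use its reading in a sensitivity analysis, and report removals by arm.

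The cost is one sentence in 6.2.2, one rule repeated in four sections, and central reading of a few specimens that are obtained anyway. No visits or subjects are added. The downside is that an occasional false-alarm removal counts as a failure, possibly more often under imiquimod because of local inflammation. The biopsy-first rule and the sensitivity analysis limit this.

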7.0 TREATMENT MODIFICATIONS: IMIQUIMOD

7.1 Dose reduction levels

7.1.1 Dose reduction for imiquimod

Treatment related toxicities will be managed by treatment interruptions and possible dose reductions of imiquimod according to the schedule described in the below Tables. Dose reductions will apply to individual subjects only. Once the dose has been reduced, it cannot be increased later.

To prevent the development of more severe adverse events, treatment related rash/skin irritation should be managed early and proactive as described in the below Tables. Table 1: Dose reduction scheme for imiquimod

HIC#: 1603017415 Protocol version 11.0

AE type and CTCAE Grade	Action	Dose reduction scheme
Figure 2 • Dermatologic or local inflammatory reactions which responds promptly to symptomatic treatment (e.g., antihistamines, NSAIDS, narcotics); prophylactic medications indicated for ≤ 24 hrs • Vulvar edema with readily apparent obscuration of anatomic architecture, obliteration of skin folds, deviation from normal anatomic contour • Any drug related AE Grade ≥3	Pause treatment until subject has recovered to Grade ≤1 or baseline¹. Resume treatment. May reduce dose according to schedule opposite. If subject has not recovered to Grade ≤1 or baseline¹ within 21 days study treatment must be permanently discontinued².	If subject was receiving 6.25 mg, resume treatment at a dose of 3.125. If subject was receiving 3.125 mg, discontinue imiquimod.

- 1 Baseline is defined as the CTCAE (version 4) Grade at the start of treatment
- In the event that the subject is deriving obvious clinical benefit according to the investigator's judgement, further treatment with imiquimod will be decided by the investigator.

In the event of any unrelated adverse events, the investigator may choose to interrupt the medication for up to 21 days, but no dose reduction should occur. If the medication is interrupted for more than 21 days, the decision to continue with imiquimod will be made by the investigator.

7.2 Management of adverse events, concomitant therapy, restrictions and rescue treatment

7.2.1 Rescue medication, emergency procedures, and additional treatment(s)

7.2.1.1 Rescue medication

Rescue medications to reverse the actions of imiquimod are not available. There is no specific antidote for overdosage. Potential adverse events should be treated symptomatically. Common adverse events of treatment with imiquimod with specified management recommendations and/or requirements include local inflammatory reactions with site itching or burning or localized edema and occasionally accompanied by dermatologic, respiratory, or infectious symptoms. To improve tolerability and the probability of clinical benefit, subjects should receive prompt and appropriate supportive care at the first signs of symptoms. Suggested treatments for AEs are described below.

7.2.1.2 Concomitant treatment(s)

Concomitant medications or therapy to provide adequate supportive care may be given as clinically necessary.

All concomitant therapy, including anaesthetic agents, vitamins, homeopathic/herbal remedies, nutritional supplements, must be recorded in the (e)CRF during the screening and treatment period, starting from the date of signature of informed consent, and ending at the EOT visit. After the EOT visit, only concomitant therapy indicated for treatment of an AE has to be reported.

HIC#: 1603017415 Protocol version 11.0

In case of major surgery (as judged by the investigator), it is recommended to stop treatment with imiquimod around one week prior to the surgery, and to restart treatment after surgery (unless surgery involves genitourinary or anogenital tracts in which case treatment should be suspended until complete wound healing achieved). If imiquimod is interrupted for more than 21 days, the decision to continue will be made by the sponsor in agreement with the investigator.

7.2.2 Management of expected adverse events

Dermatologic and local inflammatory adverse events are the most common side-effects associated with treatment with imiquimod. Respiratory symptoms are less commonly reported but can include sinusitis, upper respiratory tract infection or flu-like symptoms. Treatment of these side-effects should be proactive and should be started as early as possible after onset of symptoms.

7.2.2.1 Management of dermatologic and local inflammatory adverse events following treatment with imiquimod

Dermatologic adverse events including localized erythema, xeroderma, crusted skin, erosion or ulceration, edema, vulvar pain or pruritus can occur after a few applications of imiquimod. Although usually mild to moderate, dermatologic reactions can cause significant discomfort (Table 7.2.2.1: 2).

Table 2: Grade specific treatment recommendations for imiquimod-related dermatologic/ local inflammatory reactions:

Severity (CTCAE Grading)	Description	Intervention concerning imiquimod treatment	Specific intervention
Pain of skin			
Mild (Grade 1)	Mild pain	Continue same dose	Consider oral acetaminophen or ibuprofen
Moderate (Grade 2)	Moderate pain; limiting instrumental ADL	Continue same dose unless Grade 2 skin pain continues for ≥ 2 days (48 hours) in which case treatment must be interrupted until recovered to ≤ Grade 1 followed by dose reduction	
Severe (Grade 3)	Severe pain; limiting self care ADL	Dose interruption until recovered to ≤Grade 1 followed by dose reduction*	See Grade 2; plus: an infectious process should be ruled out with pelvic exam and cultures.
Pruritis			
Mild (Grade 1)	Mild or localized; topical intervention indicated	Continue same dose	Topical polidocanol cream. Consider oral antihistamines, e.g. diphenhydramine, dimethindene, cetirizine,

HIC#: 1603017415 Protocol version 11.0

			levocetirizine, desloratidine, fexofenadine or clemastine)
Moderate (Grade 2)	Intense or widespread; intermittent; skin changes from scratching (e.g., edema, papulation, excoriations, lichenification, oozing/crusts); oral intervention indicated; limiting instrumental ADL	Continue same dose unless Grade 2 skin pain continues for ≥ 2 days (48 hours) in which case treatment must be interrupted until recovered to \leq Grade 1 followed by dose reduction	See Grade 1 plus oral histamines; Consider topical steroids (e.g., topical hydrocortisone)
Severe (Grade 3)	Intense or widespread; constant; limiting self care ADL or sleep; oral corticosteroid or immunosuppressive therapy indicated	Dose interruption until recovered to ≤Grade 1 followed by dose reduction*	See Grade 2; plus: an infectious process should be ruled out with pelvic exam and cultures
Skin Ulceration			
Mild (Grade 1)	Combined area of ulcers < 1cm; nonblanchable erythema of intact skin with associated warmth or edema	Continue same dose	Consider oral acetaminophen or ibuprofen; consider topical polidocanol cream
Moderate (Grade 2)	Combined area of ulcers 1 - 2 cm; partial thickness skin loss involving skin or subcutaneous fat	Continue same dose unless Grade 2 skin ulcers continue to worsen after ≥ 2 days (48 hours) in which case treatment must be interrupted until recovered to ≤ Grade 1 followed by dose reduction	See Grade 1; consider topical antibiotics and additional topical analgesic treatments
Severe (Grade 3)	Combined area of ulcers >2 cm; full-thickness skin loss involving damage to or necrosis of subcutaneous tissue that may extend down to fascia	Dose interruption until recovered to ≤Grade 1 followed by dose reduction*	See Grade 2; Consider oral antibiotics and institute additional symptomatic therapy (topical or systemic) as clinically indicated. Consider dermatology consultation
Life threatening (Grade 4)	Any size ulcer with extensive destruction, tissue necrosis, or damage to muscle, bone, or supporting structures with or without full thickness skin loss	Dose interruption until recovered to ≤Grade 1 followed by dose reduction*	See Grade 3. Consider oral antibiotics
Localized (Vulvar) E	ldema		
Mild (Grade 1)	Localized to dependent areas, no disability or functional impairment	Continue same dose	Avoid prolonged dependent positions

HIC#: 1603017415 Protocol version 11.0

Moderate (Grade 2)	Moderate localized edema and intervention indicated; limiting instrumental ADL	Continue same dose unless Grade 2edema continue to worsen after	See Grade 1
		≥ 2 days (48 hours) in which case treatment must be interrupted until recovered to ≤ Grade 1 followed by dose	
		reduction	
Severe (Grade 3)	Severe localized edema and intervention indicated; limiting self care ADL	Dose interruption until recovered to ≤Grade 1 followed by dose reduction*	See Grade 1; Consider Foley catheter placement if urethral obstructed

^{*} If despite optimal supportive care and a treatment interruption, dermatologic reactions does not resolve to CTC AE Grade ≤ 1 within 21 days, treatment with imiquimod must be permanently discontinued. In the event that the subject is deriving obvious clinical benefit according to the investigator's judgement, further treatment with imiquimod will be decided by the investigator.

7.2.2.2 Management recommendations for respiratory AEs following treatment with Imiquimod Respiratory adverse events including sinusitis, flu-like symptoms, upper respiratory tract infection can occur, although usually mild to moderate (Table 7.2.2.2: 3).

Table 3: Grade specific treatment recommendations for imiquimod-related respiratory reactions:

Severity	Description	Specific intervention
(CTCAE Grading)		
Upper respiratory in	fection	
Mild (Grade 1)	-	-
Moderate (Grade 2)	Moderate symptoms; oral intervention indicated (e.g., antibiotic, antifungal, antiviral)	Consider oral antibiotic, antifungal or antiviral; Consider anti-pyretic
Severe (Grade 3)	IV antibiotic, antifungal, or antiviral intervention indicated; radiologic, endoscopic, or operative intervention indicated	See Grade 2; if not improving within 48 hours of initiation of oral medication, consider IV formulation and also radiologic imaging
Life-threatening (Grade 4)	Life-threatening consequences; urgent intervention indicated	IV antibiotic therapy, radiologic imaging, evaluate for other systemic infections, hospitalization to monitor progress and if urgent respiratory interventions required
Sinusitis		
Mild (Grade 1)	-	
Moderate (Grade 2)	Localized; local intervention indicated (e.g., topical antibiotic, antifungal, or antiviral)	Consider oral antibiotic, antifungal or antiviral; Consider anti-pyretic
Severe (Grade 3)	IV antibiotic, antifungal, or antiviral intervention indicated;	See Grade 2; if not improving within 48 hours of initiation of oral medication, consider IV formulation and also radiologic imaging

HIC#: 1603017415 Protocol version 11.0

CIN 2/3

	radiologic, endoscopic, or operative intervention indicated	
Life threatening	Life-threatening consequences;	See Grade 3
(Grade 4)	urgent intervention indicated	
Death (Grade 5)	Death	
Flu like symptoms		
Mild (Grade 1)	Mild flu-like symptoms present	Consider anti-pyretic
Moderate (Grade 2)	Moderate symptoms; limiting instrumental ADL	See Grade 1
Severe (Grade 3)	Severe symptoms; limiting self care ADL	See Grade 1

^{*} If despite optimal supportive care and a treatment interruption, respiratory reactions does not resolve to CTC AE Grade ≤ 1 within 21 days, treatment with imiquimod must be permanently discontinued. In the event that the subject is deriving obvious clinical benefit according to the investigator's judgement, further treatment with imiquimod will be decided by the investigator.

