Vaginal suppositories will be self-applied by the subjects in the evening right after going to bed. Subjects will be advised not to have sexual intercourse during the nights in which they applied vaginal suppositories and to perform a vaginal douche in the morning. Subjects will be instructed to suspend the application of vaginal suppositories during the first 3 days of their menses. Subjects will be advised to keep the study medication refrigerated. In case of persistent side effects in subjects of the imiquimod group, the dose of the study medication will be modified and participants will receive vaginal suppositories containing only 50% of the original imiquimod dose (vaginal suppositories containing 3.125 mg imiquimod).

Missed doses of imiquimod can be made up the following day. Otherwise, the dose must be skipped and subjects should take the next scheduled dose at the usual time.

Imiquimod will be dispensed in boxes containing 18 vaginal suppositories (treatment weeks 1-8) at the beginning of the treatment course. During follow up visit at week 8 (see below), subjects will be provided a new box of 24 vaginal suppositories to complete treatment course for weeks 9-16. Study drug will be prescribed by the investigator and may be dispensed either by the investigator or study staff.

HIC#: 1603017415 Protocol version 11.0

CIN 2/3

11

(3) Imiquimod + HPV vaccine: At the baseline visit, this group will be instructed about the correct method of self-application of imiquimod 6.25mg as a vaginal suppository as described above, storage of medication, possible side effects. Subjects will be provided a diary and case report form to record vaginal suppository application and side effects will be recorded per NCI Common Terminology Criteria for Adverse Events (CTCAE 4.0). In addition, all women (regardless of age) will be administered a dose of the HPV vaccine on day of enrollment (regardless of previous HPV vaccination history). Women previously unvaccinated will receive an additional booster dose at 8 weeks. Local pain will be assessed with a visual analog scale immediately after vaccine administration and 5 minutes later. Subjects will be provided a separate case report form to record vaccine side effects per CTCAE 4.0.

Missed doses of imiquimod can be made up the following day. Subjects are encouraged to complete taking all prescribed doses. If additional time is required toward this goal of treatment, the scheduled dosing period may be extended.

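### In Table 2 the Grade 2 pruritus row uses skin pain as its trigger for interrupting imiquimod, so read literally it keeps a woman with persistent Grade 2 itch and no pain on the same dose

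*Combined protocol and SAP*

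**What the plan says.** Section 7.1.1 says that imiquimod toxicity is handled by interruption and possible dose reduction under the tables that follow, and that skin irritation is to be managed early. Table 2 in section 7.2.2.1 gives the graded rules for dermatologic and local inflammatory reactions.

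For Grade 2 pruritus the description begins "Intense or widespread; intermittent; skin changes from scratching" and goes on to oral treatment and limits on instrumental activities. The dosing instruction in that row is "Continue same dose unless Grade 2 skin pain continues for ≥ 2 days (48 hours) in which case treatment must be interrupted", with dose reduction after recovery. The same instruction stands in the Grade 2 row for pain of skin.

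The other two Grade 2 rows name their own event. For ulceration: "Continue same dose unless Grade 2 skin ulcers continue to worsen after ≥ 2 days (48 hours) in which case treatment must be interrupted". For vulvar edema: "Continue same dose unless Grade 2edema continue to worsen after", with the same 48-hour limit. Grade 3 pruritus, described as "Intense or widespread; constant; limiting self care ADL or sleep", leads to interruption and then reduction with no condition about pain.

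Two other provisions bear on the case. Section 6.2.1 says: "In case of persistent side effects in subjects of the imiquimod group, the dose of the study medication will be modified", and sets the reduced suppository at 3.125 mg. Table 1 in section 7.1.1 pauses treatment for "Dermatologic or local inflammatory reactions which responds promptly to symptomatic treatment", among other entries.

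**The concern.** The trigger in the pruritus row is a different symptom from the one that the row grades. A woman can have Grade 2 itch for weeks, never have Grade 2 skin pain, and never meet the condition for interruption in the row that describes her.

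Itching is among the common imiquimod reactions named in sections 7.2.1.1 and 7.2.2.1, so the row is likely to be used. The row is also an operative rule: it says when treatment must stop, and section 7.1.1 sends sites to the tables. Some sites would follow the cell as printed, others would infer what was meant, and others would turn to section 6.2.1. Under section 7.1.1 a reduced dose cannot be raised again, so the choice is not easily undone.

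What is at stake is patient safety, and the comparability of the tolerability data. Tolerability is a secondary objective (section 1.2.3), and section 10.13 assesses it partly by how often and for how long treatment is interrupted.

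**Working it through.** No arithmetic applies. The check is to compare the Grade 2 rows of Table 2 with each other, and then with the two rules outside the table.

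**Step 1. The Grade 2 rows of Table 2.**

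| Row | Event in the description | Event in the interruption trigger | Match |
|---|---|---|---|
| Pain of skin | Pain | Skin pain lasting 48 hours or more | Yes |
| Pruritus | Itch and changes from scratching | Skin pain lasting 48 hours or more | No |
| Skin ulceration | Ulcers | Ulcers worsening after 48 hours or more | Yes |
| Vulvar edema | Edema | Edema worsening after 48 hours or more | Yes |

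Three of the four rows use their own event, and the pruritus row repeats the pain row. It is a separate cell with its own description and its own list of interventions, so the likeliest explanation is text carried over from the row above.

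**Step 2. Apply the row literally.** Take a woman with Grade 2 itch lasting more than 48 hours, no skin pain, and no ulcer or edema that would bring in another row. The condition for interruption is not met, so the instruction is to continue the same dose. Within Table 2, itch alone first leads to interruption at Grade 3.

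**Step 3. Section 6.2.1.** Persistent Grade 2 itch is on any ordinary reading a persistent side effect, and the text is mandatory: the dose is lowered to 3.125 mg. This supplies the reduction. It does not say which grade counts, how long is persistent, or whether treatment is paused first. It therefore contradicts the literal pruritus row without giving sites the rule that the row should have contained.

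**Step 4. Table 1.** Its dermatologic entry sits beside a separate entry for any drug-related event of Grade 3 or higher. The dermatologic entry would be largely redundant unless it reached below Grade 3, so it probably covers some Grade 2 reactions. It gives antihistamines as an example treatment, and Table 2 recommends these for itch. But it is limited to reactions that respond promptly, with preventive medication needed for no more than 24 hours. Itch that persists is hard to fit to that wording. Table 1 may help, but it does not settle the case.

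**Step 5. Effect on the analyses.** The primary comparison in section 15.5 uses the modified ITT set, analyzed by assigned treatment. Section 15.2 defines that set by valid baseline data, at least one dose and a valid post-baseline outcome. Neither membership nor the test depends on whether a dose was paused or reduced. The per-protocol set does depend on it, since section 15.2 lists dose modification as an example of a deviation, but section 15.5 offers that set only as an optional sensitivity analysis.

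**The case against.** The strongest reply is that the protocol as a whole already protects this woman. Section 6.2.1 requires the dose to be lowered for persistent side effects, Table 1 probably reaches some reactions below Grade 3, and Table 2 still gives her antihistamines and possibly topical steroids. On that view the cell is an editorial slip that any investigator would see through.

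Much of this stands. A reader might infer that the protocol has no route to a lower dose for persistent Grade 2 itch; section 6.2.1 shows that it has one. A reader might also try to express the error as excess imiquimod exposure, by comparing full with halved dosing from some week onward. The documents do not support such a figure. Section 6.2.1 already halves the dose for persistent side effects, so the difference would arise only if that section were ignored. The week of onset and the length of any pause would have to be assumed, and no rate of Grade 2 pruritus is given. Even the number of doses lost to a pause is unclear: the provision that "If additional time is required toward this goal of treatment, the scheduled dosing period may be extended" appears only under the combination arm, while the imiquimod-only text says that a dose not made up the next day is skipped.

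What does not stand is that the other provisions repair the cell. They conflict with its literal instruction, and neither supplies a graded, timed trigger for itch.

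**Conclusion.** The point holds as a drafting error in one operative cell. Under Table 2 as printed, persistent Grade 2 itch without pain leads to no interruption or reduction, and this conflicts with section 6.2.1. It is minor. The effect is confined to consistent safety management and to the tolerability data on interruptions; the sample size and the primary analysis are unaffected.

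The conclusion rests on two readings: that the pruritus row was meant to name its own event, as the ulceration and edema rows do, and that the 48-hour limit was intended for it. The first is well supported by the layout of the table. The second is the natural reading, since the limit is already in the cell. How many subjects would be affected cannot be estimated from the documents.

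**What to change.** In Table 2, Grade 2 pruritus row, replace *Grade 2 skin pain* with *Grade 2 pruritus*, and leave the 48-hour limit, the recovery condition and the dose reduction as they are. The row then agrees in direction with section 6.2.1 and supplies the grade, duration and pause that section lacks.

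The cost is one phrase, issued as a protocol amendment through the IRB. Visits, sample size and statistical methods do not change. There is one small downside: a few more subjects may have their dose interrupted or reduced, and these may leave the optional per-protocol set because dose modification is listed there as a deviation.
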